9. BLINDING

The study is not blinded.

10. STUDY ASSESSMENTS

Mankoski Pain Scale assessments are conducted during the study for a period of 2 weeks of treatment with OrthoCor Active system or Standard of Care. The enrolled participant will have a treatment period from Day 0 through Day 14 when the study ends, and a research extension period and assessments are conducted for a period of additional 2 weeks (see Table 1. Schedule of Assessments in protocol).

The primary endpoints as well as safety analyses will be evaluated at study end.

Exploratory analyses will be assessed after the extension period of additional 2 weeks.

11. GENERAL CONSIDERATIONS

11.1. General Methods

A repeated measures ANOVA will be utilized to assess statistical differences between the active and sham devices. A test of normality will be performed. If the data is not shown to be normally distributed, nonparametric methods may be used. All hypotheses are performed at an alpha equal to 0.05.

11.2. Analysis Population

The following analysis populations will be defined for the study:

Intent-to-Treat (ITT) Population – The ITT population will consist of all enrolled subjects that completed any treatment.

Per-Protocol (PP) Population – The PP population will consist of all enrolled subjects with 2 weeks of treatment and without any critical data missing and data collected per protocol.

Safety Population – The safety population will consist of all enrolled subjects that have had treatment with active OrthoCor Active System.

The analysis of efficacy data will be conducted on the ITT and PP populations.

All safety analyses will be performed on the safety population.

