11.6 Safety

All adverse events for subjects in the safety population will be reported.

- Serious Adverse Events
- Non-serious Adverse Events Device Related Adverse Event
- Device Related Serious Adverse Events

Results will include the number of subjects experiencing each type of event as well as the number of events.

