5. STUDY OBJECTIVES AND ENDPOINTS

The primary safety and efficacy objectives are:

Safety endpoint of this study will be the adverse events reported with the OrthoCor Active System after 2 weeks of use.

Efficacy endpoint of this study will be the comparison of the OrthoCor Active System pain assessment scores to the Standard of Care (SOC) intervention after 2 weeks of use. The primary effectiveness endpoint of this study is the change from baseline of the OrthoCor Active System compared to the SOC intervention.

The exploratory objectives, for publication only, are comparison of the performance of the OrthoCor Active System to standard of care after additional 2 weeks of use.

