6. SUBJECT POPULATION

The target population is both female and male, over the age of 18 years pain in the superficial tissue at sites such as ankle, back, knee, wrist, elbow, shoulder, foot, or neck who meet inclusion criteria and do

not meet any exclusion criteria from the protocol. The participants will be selected from the population selected by the Principal Investigator at each of the 5 participant US sites after passing the screening and eligibility assessments per protocol.

As part of exploratory research extension, patients using the OrthoCor Active system will have the opportunity to continue the trial for an additional 2 weeks. Participants assigned SOC have the opportunity to cross-over using the OrthoCor Active system for the additional 2 weeks. Participation in the exploratory extension is optional.

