12.3. Safety Variables

This is a non-significant risk study. Because no procedures are required to perform the investigational study, safety will be monitored via the reported Adverse Events, in this study. The descriptive table of Adverse Events, within protocol, will be the extent of safety reporting.

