12.8. Safety

All adverse events for participants in the safety population will be reported.

- Serious Adverse Events
- Non-serious Adverse Events Device Related Adverse Event
- Device Related Serious Adverse Events

Results will include the number of participants experiencing each type of event as well as the number of events.

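### The safety population holds device-treated subjects only, so standard-of-care subjects who never use the device appear in no adverse event table, and nothing assigns crossover subjects' events to a treatment or period

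*SAP*

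**What the plan says.** **Population.** SAP 11.2 defines the set by exposure to the device: "The safety population will consist of all enrolled subjects that have had treatment with active OrthoCor Active System". It then adds: "All safety analyses will be performed on the safety population".

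**Reporting.** SAP 12.8 says "All adverse events for participants in the safety population will be reported". Protocol 11.6 uses the same restriction, and the protocol gives no definition of a safety population of its own. SAP 12.3 closes the list: "The descriptive table of Adverse Events, within protocol, will be the extent of safety reporting".

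**Endpoint and timing.** SAP 5 words the safety endpoint as "adverse events reported with the OrthoCor Active System after 2 weeks of use". SAP 10 places the end of the study at Day 14, has safety evaluated then, and leaves exploratory analyses until after the extension. SAP 11.3 times the final analysis to the point when every enrolled subject has finished two weeks.

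**Crossover.** SAP 6 allows it: "Participants assigned SOC have the opportunity to cross-over using the OrthoCor Active system for the additional 2 weeks". Protocol 9.4 adds a conditional route. If the study is declared complete early, the remaining SOC subjects may move to the device whether or not they have entered the extension.

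**Collection.** Protocol 10.1 defines an AE without regard to device relation. Protocol 10.2 records all AEs from day 1 with no restriction by arm. The AE row of Table 1 in protocol 9.5, however, is limited to events related to the test device; it is marked for Days 1-14 and for the extension.

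**The concern.** Half of the planned subjects are assigned to SOC, and the safety plan has no place for what happens to them on SOC. A device-arm table of skin irritation, soreness or any other event cannot then be read against the background rate in comparable subjects followed in the same way. In an open-label trial that comparison matters, because the investigator who judges relatedness knows which treatment was used.

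The second difficulty is that membership can be acquired late. An SOC subject who takes the device becomes a member, and all of a member's AEs are reported. Such a subject's SOC-period events could then sit in a table meant to describe the device, and extension events could sit beside those from the randomised two weeks.

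**Working it through.** The documents state no AE rate, safety denominator or safety precision, so there is no safety figure to reproduce. The check is a comparison of sections, followed by denominators and an illustration.

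**1. Who reaches an AE table.** SAP 11.2 admits only device-exposed subjects, SAP 12.8 and protocol 11.6 report AEs for that set, and SAP 12.3 allows no other safety output. No other section supplies an SOC table. An SOC subject who never uses the device is therefore in none.

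**2. Denominator.** Inputs: up to 50 subjects per arm (SAP 7). Crossover is optional and its uptake c is not given, so c runs from 0 to 1. Safety N = 50 + 50c.

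| c | Safety N | SOC subjects in no AE table | Crossover share of safety set |
|---|---|---|---|
| 0 | 50 | 50 | 0% |
| 0.5 | 75 | 25 | 33% |
| 1 | 100 | 0 | 50% |

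The two extremes are alternatives. Fifty SOC subjects outside the set requires no crossover; a denominator of 100 requires full crossover.

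**3. Does the timing text exclude crossover?** With a strict Day 14 cut as SAP 10 suggests, no scheduled crossover has occurred, N is the device arm (up to 50), and the extension does not enter. Three things leave this unsecured:
- SAP 5 counts two weeks of use, which a crossover subject completes during the extension.
- At the final analysis (SAP 11.3), subjects enrolled early may already have extension AEs, and no data cut is written.
- Under the protocol 9.4 rule, if triggered, a move to the device could come before Day 14.

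**4. Illustration of what pooling would do.** These rates are assumptions, not document figures. Let p be the risk of at least one AE per two weeks, constant and independent between periods, with all device subjects continuing and all SOC subjects crossing over.

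- On-device events only: [50(1 - (1 - p)²) + 50p]/100
- Adding SOC-period events of crossover subjects at the same risk: [50(1 - (1 - p)²) + 50(1 - (1 - p)²)]/100

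At p = 10%, 1 - 0.9² = 0.19. The first gives (9.5 + 5)/100 = 14.5% and the second (9.5 + 9.5)/100 = 19.0%, against 10.0% for the device arm in Days 0-14.

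| Assumed p | On-device only | With SOC-period events |
|---|---|---|
| 2% | 3.0% | 4.0% |
| 5% | 7.4% | 9.8% |
| 10% | 14.5% | 19.0% |
| 20% | 28.0% | 36.0% |

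The figure can also fall. Suppose no device subject continues, all SOC subjects cross over, and their on-device risk is q. The pooled value is (50p + 50q)/100. With p = 10%, q = 5% gives (5 + 2.5)/100 = 7.5%, and the limit q = 0 gives 5/100 = 5%. No section supports a particular q; the point is only that the direction is not fixed.

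**5. Are SOC events collected?** Protocol 10.1 and 10.2 say all AEs are. Table 1 schedules only device-related ones, and one sentence in protocol 10.2 ties documentation to the time after product use. An SOC column built on the Table 1 reading could be nearly empty and would wrongly favour SOC.

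**The case against.** The strongest defence is that the set matches the endpoint. The safety endpoint concerns the device alone, comparative safety is not among the objectives in protocol 7, and this is a non-significant-risk study of a device already cleared for commercial use. Relatedness is judged for each event, and device-related events have their own categories in SAP 12.8. Worsening pain is already compared between arms through the efficacy endpoint. This stands as a reason for moderate weight. It does not supply an SOC table, and unblinded relatedness judgements are a weak substitute for one.

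A reader might infer that the plan pools the randomised period with the extension. The documents do not say so: SAP 5 and SAP 10 point to two weeks and Day 14, and SAP 11.3 times the exploratory analysis separately. What stands is that no cut, attribution rule or split by period is written.

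A reader might also infer that SOC events can never be tabulated. That fails for crossover subjects, whose SOC-period events could enter through SAP 12.8, although unlabelled as such.

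Finally, it is tempting to present a fall from 5/50 to 5/100 as dilution. That needs a zero event rate among crossover subjects, which nothing supports. If it did occur, 5/100 would be a fair proportion for the first two weeks of use among all exposed subjects.

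**Conclusion.** The point holds in a limited form. Followed as written, the plan gives no AE tabulation for SOC subjects who never use the device: up to 50 of 100 if none crosses over, fewer as crossover rises. This rests on the text alone and is unaffected by how the Day 14 timing is read.

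Mixing of treatments and periods in the device table is a possibility left open by an exposure-only definition. It is not something the SAP plans. A strict Day 14 cut would remove the scheduled-extension part of that risk, but not a crossover before Day 14 under protocol 9.4. Without a cut, the denominator lies between 50 and 100, and the effect on the reported rate has no fixed sign; the percentages in the illustration depend on assumed risks and uptake.

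The point concerns the completeness and clarity of safety reporting. It does not touch the efficacy comparison. It should be corrected because a clearer rule is available at little cost.

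**What to change.** In SAP 11.2, define the safety set as all enrolled subjects who received either intervention, analysed by the treatment actually received. In SAP 12.3 and 12.8:
- make the primary safety table AEs in Days 0-14 by arm, each arm with its own denominator (up to 50 each);
- assign every event to the treatment in use at its onset, and state the data cut;
- show extension events in separate columns for continued device use and for crossover to the device.

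Align protocol 11.6 with the new definition. Reconcile the AE row of protocol Table 1 with protocol 10.1 and 10.2, so that all AEs are captured in both arms. Until that is settled, an SOC column would not be interpretable.

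The cost is SAP and schedule wording, a few extra table columns and possibly some additional AE recording in the SOC arm. Treatment and sample size do not change. If SOC events have so far been collected under the narrower Table 1 reading, the report should say so beside the SOC column.

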11.3. Timing of Analyses

The final analysis will be performed after all enrolled participants have completed the 2 weeks treatment period.

The additional analysis for exploratory research will be performed after all enrolled participants completed the 2 weeks of treatment and any of the additional exploratory days and up to 2 weeks.

12. STATISTICAL ANALYSIS

The data consists of multiple repeated measures and will be checked for normalcy and sphericity, and primary analysis will consist of ANOVAs for repeated measures and with other secondary analysis as appropriate for secondary hypotheses. Nonparametric methods will be used if the data is not normally distributed.

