9.5 Study Schedule of Assessments

In the evening of each day the subject should rate their pain using the provided scale and record their rating in the eDiary. Refer to Table 1 Schedule of Assessments.

Table 1. Schedule of Assessments

Assessments	Screening/Baseline (Day 0)	Day 1 - 14	Research Extension (if applicable) Day 15 – 30
Inclusion/Exclusion Criteria	X		
Demographics	X		
Surgical Date	X		
Pain Assessment	X	X	X
Self-reported Pre-Existing Conditions*	X*		
OrthoCor Active System/SOC Intervention Use		X	X
Device Information	X		
OrthoPod Information	X	X	X
Concomitant Pain Medication Use	X	X	X
Adverse Event, related to the test device		X	X
Pregnancy test for WOCBP	X		

* Information to be collected if available

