11.0 STATISTICAL ANALYSIS

The primary effectiveness endpoint of this study is the change from baseline of the OrthoCor Active System compared to the SOC intervention results after 14 days.

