7. SAMPLE SIZE

The sample size estimates are calculated assuming a binomially distributed response of improvement or no improvement. Without any a priori estimates, the most conservative estimate (widest interval) is using a baseline for the standard of care (SOC) of 50% improvement. The null hypothesis for a non-inferiority study is that the experimental treatment is inferior to the standard of care. The alternative hypothesis is that the experimental treatment is non-inferior to the standard of care.

The sample size per group is based on the comparison of two proportions with baseline proportion of 50% for the experimental treatment assuming a 50% response for SOC and a non-inferiority margin of 10% assuming 90% power. The assumed confidence is 95% or a type 1 error rate of 5%.

The study will enroll 100 subjects, up to 50 using the OrthoCor Active System and up to 50 using the Standard of Care (SOC) intervention. The patients will be enrolled consecutively at the participant site until enrollment is met. The CRO will stratify the arms (OrthoCor Active System vs SOC) by selecting the arm alternatively.

For the exploratory assessments, the 50 subjects who received SOC will have the opportunity to cross-over and use the OrthoCor Active system.

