12.1. Primary Endpoints

The primary endpoints of this study will be to compare the reduction of pain symptoms from baseline on the Mankoski Pain Scale after 2 weeks of treatment with the OrthoCor Active System device and Standard of Care.

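### The SAP checks sphericity with no stated consequence and names neither the ANOVA term nor the error term for the 2-week change, so type I error could exceed 5% if daily ratings are serially correlated

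*SAP*

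**What the plan says.** - **Model and check.** SAP 12 says that the data "will be checked for normalcy and sphericity, and primary analysis will consist of ANOVAs for repeated measures". SAP 11.1 also names a repeated-measures ANOVA, without mentioning sphericity.
- **Consequence of a failed check.** Only non-normality has one. SAP 12: "Nonparametric methods will be used if the data is not normally distributed". SAP 11.1 makes the same step optional: "If the data is not shown to be normally distributed, nonparametric methods may be used". Neither section gives an epsilon correction, a multivariate test or another model for a failed sphericity check.
- **Endpoint.** SAP 12.1 sets out to "compare the reduction of pain symptoms from baseline on the Mankoski Pain Scale after 2 weeks of treatment" in the two arms. Protocol 11.0 describes "the change from baseline of the OrthoCor Active System compared to the SOC intervention results after 14 days".
- **Data.** Protocol 9.5: "In the evening of each day the subject should rate their pain using the provided scale". Table 1 there has a pain assessment at Day 0 and on Days 1 to 14, which makes 15 ratings in the main period.
- **Error rate.** SAP 11.1: "All hypotheses are performed at an alpha equal to 0.05". Sidedness is not stated.

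The SAP does not say which days enter the ANOVA, which of its terms is the primary test, or what error term a Day 14 comparison would use. Neither document gives a standard deviation or a within-subject correlation for the pain score.

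**The concern.** Sphericity matters to the within-subject tests of a univariate repeated-measures ANOVA with three or more time levels. Those tests use a single subject-by-time error, which reflects the average correlation over all pairs of days. Daily pain ratings plausibly correlate more strongly on neighbouring days than two weeks apart. The endpoint compares the two days that are furthest apart. If their correlation is below average, a pooled error understates the variance of exactly this comparison. The test then rejects too often and the confidence interval is too short. The group-by-time F test is also too liberal when sphericity fails and no correction is applied.

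The type I error of the primary efficacy comparison is at stake. A check that leads to no action gives no protection, and an unnamed test term leaves a choice open until after the data are seen.

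**Working it through.** **Inputs from the documents.** 15 ratings (Protocol Table 1), up to 50 subjects per arm (SAP 7), alpha 0.05 (SAP 11.1).

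**Assumptions.** Two-sided test, equal variance on each day, normal and complete data, and the correlation patterns below. The open-label design and the alternating allocation are not modelled.

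**Formula.** Let r be the Day 0 to Day 14 correlation and m the mean correlation over the 105 pairs of days. The change has variance 2σ²(1 − r). The pooled error treats it as 2σ²(1 − m). The ratio is R = (1 − r)/(1 − m), and the actual type I error is about 2 × [1 − Φ(1.96/√R)].

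**The plan's own figure.** Under compound symmetry r = m, so R = 1 and the result is 2 × [1 − Φ(1.96)] = 5%, as stated.

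**Serial correlation.** With AR(1) correlation ρ, r = ρ¹⁴ and m = (1/105) × Σ(15 − d)ρ^d for d = 1 to 14. At ρ = 0.8, r = 0.044 and m = 0.388, so R = 0.956/0.612 = 1.56. Then 1.96/√1.56 = 1.57, and the type I error is 11.7%.

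The last three columns come from simulation under the null (10,000 runs per scenario, 50 per arm).

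| ρ | R | Contrast, pooled error (formula) | Contrast, pooled error (simulated) | Group-by-time F, uncorrected | Contrast, own error |
|---|---|---|---|---|---|
| 0.5 | 1.14 | 6.7% | 6.7% | 7.7% | 5.0% |
| 0.7 | 1.34 | 9.1% | 9.0% | 11.2% | 4.9% |
| 0.8 | 1.56 | 11.7% | 11.6% | 12.1% | 5.0% |
| 0.9 | 1.95 | 16.1% | 16.1% | 13.9% | 5.2% |
| 0.95 | 2.25 | 19.1% | 19.8% | 14.8% | 5.2% |

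The interval on the pooled error has 1/√R of its proper width: 94%, 86%, 80%, 72% and 67% down the rows.

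**Other patterns for the pooled-error contrast (formula).**
- Adding a random intercept changes nothing, because it scales 1 − r and 1 − m alike.
- A random intercept that carries half the variance, plus AR(1) 0.3, gives 5.7%.
- Independent rating noise equal in variance to the AR(1) part changes R to (1 − 0.5r)/(1 − 0.5m). The result is 5.8%, 6.7%, 7.5%, 8.2% and 7.7% at ρ = 0.5, 0.7, 0.8, 0.9 and 0.95.
- A baseline correlated 0.4 with later days, which correlate 0.7 among themselves, gives 14.0%.

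**Tests that hold their level (simulated, all patterns).**
- The group main effect gives 4.5% to 5.4%.
- The contrast on its own error gives 4.5% to 5.4%.
- The group-by-time F with Greenhouse-Geisser correction gives 3.8% to 5.2%. This correction does not alter the standard error of a single contrast tested on the pooled error.
- If only Day 0 and Day 14 enter, there are two levels, sphericity holds trivially and the test is at 5%.

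**Smaller sample.** At 32 per arm, the size at which Protocol 9.4 allows the study to be considered completed, the simulated pooled-error contrast gives 9.3% (ρ = 0.7) and 15.9% (ρ = 0.9).

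**The case against.** A reader might infer that the SAP pools one error over 15 ratings and that its primary test therefore runs well above 5%. The documents do not support that. They name a family of models, not a test. Large inflation of the contrast needs four things together: all 15 ratings enter, the test is the Day 0 to Day 14 contrast, it uses the pooled error, and two-week correlation is well below the average. Removing any one of these shrinks or removes the inflation of that contrast. The larger figures also assume no independent day-to-day rating noise, and a realistic diary has some. Finally, if the data are not normal, the ANOVA may not be the test that is run at all.

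All of this stands as a limit on the size of the problem. It does not remove the gap:

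- A sphericity check has meaning only for the univariate method with at least three time levels, so the SAP's own wording points towards the exposed analysis.
- The group main effect is safe, but it averages over all the days entered, so it does not measure the 2-week change from baseline.
- The terms that do bear on change are the group-by-time interaction, exposed if uncorrected, and the Day 14 contrast, exposed if tested on the pooled error.
- The nonparametric route is triggered by non-normality, so it gives no protection when sphericity alone fails.

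**Conclusion.** The concern holds as a gap in specification with a conditional effect on type I error. The sphericity check has no consequence, and neither the ANOVA term nor the error term for the 2-week change is named.

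Under assumed AR(1) correlations of 0.5 to 0.95, type I error is about 7% to 19% for a Day 14 contrast on the pooled error and about 8% to 15% for an uncorrected group-by-time F. With independent noise as large as the serial part, the contrast gives about 6% to 8%. It is 5% under compound symmetry, for the group main effect, or with a contrast-specific error.

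The documents give no correlations, so it cannot be said that the stated 5% is missed, only that the plan does not secure it. The change is still worth making before the analysis, because a method that meets the stated endpoint directly is available at almost no cost.

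**What to change.** In SAP 11.1 and 12, replace the primary repeated-measures ANOVA with an ANCOVA of the Day 14 (end-of-treatment) Mankoski score on arm and baseline score. It uses one outcome per subject, so sphericity does not arise and the check can go. Bring the nonparametric rule into line in the same edit, since it is optional in one section and firm in the other.

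If the repeated-measures ANOVA is kept as supportive, apply Greenhouse-Geisser to its within-subject F tests and give the Day 14 contrast its own error.

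If a mixed model is preferred, state a fallback covariance structure. An unstructured matrix over 15 ratings has 15 × 16/2 = 120 parameters, or 14 × 15/2 = 105 with baseline as a covariate, for at most 100 subjects. The data may not support it, so it should not be the lead option.

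The cost is SAP wording and a few lines of code. Baseline and Day 14 scores are already collected, so no new data are needed.

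### The primary repeated-measures ANOVA names no Day-14 contrast, no deciding effect and no baseline covariate, so the plan does not fix a test of its stated endpoint

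*SAP*

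**What the plan says.** **Endpoint.** Protocol section 11.0 defines it as the "change from baseline of the OrthoCor Active System compared to the SOC intervention results after 14 days". SAP section 12.1 agrees: the aim is to "compare the reduction of pain symptoms from baseline on the Mankoski Pain Scale after 2 weeks of treatment" between the device and SOC. Both describe one between-arm contrast at one time.

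**Data.** Protocol section 9.5 asks for a pain rating at Day 0 and then daily: "In the evening of each day the subject should rate their pain using the provided scale and record their rating in the eDiary". That makes 15 ratings per subject, Days 0 to 14.

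**Method.** SAP section 12 states: "The data consists of multiple repeated measures and will be checked for normalcy and sphericity", and that the "primary analysis will consist of ANOVAs for repeated measures". SAP section 11.1 states: "A repeated measures ANOVA will be utilized to assess statistical differences between the active and sham devices". It adds: "All hypotheses are performed at an alpha equal to 0.05". The only fallback given is nonparametric methods if the data are not normal.

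**Not stated anywhere.** The documents do not say whether the outcome is the raw score or the change score, or which days enter the model. They do not say whether the group effect, the group-by-time interaction or a Day-14 contrast decides. They give baseline no role as a covariate and do not say what follows if sphericity fails. The trial also has no sham device; its comparator is SOC.

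**The concern.** A repeated-measures ANOVA on daily scores produces two between-arm tests by default: a group effect averaged over the days in the model, and an omnibus group-by-time test. Neither is the Day-14 difference in change. If one of them is reported as the primary result, its p-value and estimate belong to a different question from the endpoint, and the gap depends on how the effect develops over the two weeks.

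The trial is open label and several F-tests would be available, so an unnamed deciding test also leaves room to choose it after the data are seen. The baseline score, already collected, is not assigned to improving precision. If the interaction decides and sphericity fails, the plan does not say how the 5% level is kept.

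**Working it through.** **Inputs from the documents:** up to 50 subjects per arm, 15 ratings, alpha 0.05 (taken as two-sided, since sidedness is not stated). **Assumed, because the documents give no SD, effect or correlation:** a Day-14 effect of 0.6 SD, several effect profiles and several correlation patterns. There is no power figure in the plan for this analysis to reproduce; the SAP's sample size is for a binary response.

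**1. What the group effect estimates.** With Days 0 to 14 in the model, it is the mean of the 15 daily differences. As a fraction of the full effect (for the first four profiles, the Day-14 effect):

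- Constant from Day 1: 14/15 = 0.93
- Linear to Day 3, then flat: (1/3 + 2/3 + 12)/15 = 13/15 = 0.87
- Linear to Day 14: 7.5/15 = 0.50
- Starting in week 2, linear over Days 8–14: 4/15 = 0.27
- Full at Day 1, falling linearly to zero at Day 14: 7/15 = 0.47, although the Day-14 difference is 0

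Using change scores on Days 1–14 alters this little: 1.00 for the constant profile and 7.5/14 = 0.54 for the linear one.

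**2. Power at equal correlation r = 0.5 between all days, in SD units.**

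- Group effect: variance (1 + 14r)/15 = 0.533; SE = √(2 × 0.533/50) = 0.146
- Day-14 change score: variance 2(1 − r) = 1.00; SE = 0.200; 0.6/0.200 = 3.00, power 0.84
- Day-14 ANCOVA on baseline: variance 1 − r² = 0.75; SE = 0.173; 0.6/0.173 = 3.46, power 0.93

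| Profile | Group effect / SE | Power, group effect | Rejection rate, omnibus group-by-time (Greenhouse-Geisser, simulated) |
|---|---|---|---|
| Constant | 0.56/0.146 = 3.83 | 0.97 | 0.71 |
| Linear | 0.30/0.146 = 2.05 | 0.53 | 0.92 |
| Week-2 onset | 0.16/0.146 = 1.10 | 0.19 | 0.98 |
| Early, gone by Day 14 | 0.28/0.146 = 1.92 | 0.48 | 0.95 |

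In the last row the Day-14 difference is zero. Both default tests still reject often, while a Day-14 analysis rejects at 5%.

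**3. Other correlation patterns (power, group effect against Day-14 ANCOVA).**

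| Pattern | Linear profile | Day-3 plateau |
|---|---|---|
| AR(1), 0.5 | 0.94 vs 0.84 | 1.00 vs 0.84 |
| AR(1), 0.9 | 0.46 vs 0.86 | 0.90 vs 0.86 |
| Random intercept 0.5 plus AR(1) 0.5 | 0.49 vs 0.93 | 0.92 vs 0.93 |

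The ordering changes with both profile and correlation.

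**4. Type I error of the omnibus group-by-time test** (simulated, no true effect, 50 per arm, 15 ratings). Uncorrected, it is about 8–15% under AR(1) and random-intercept-plus-AR(1) errors, and about 4–6% under compound symmetry. With Greenhouse-Geisser it is about 3–5% in every pattern.

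**5. Baseline adjustment.** The ratio of ANCOVA variance to change-score variance is (1 − r²)/(2(1 − r)) = (1 + r)/2. At r = 0.3, 0.5 and 0.7 this is 0.65, 0.75 and 0.85, a reduction of 35%, 25% and 15%.

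**The case against.** **The SAP may intend a Day-14 contrast.** A reader might infer that the planned ANOVA cannot test the endpoint. The documents do not support that. Section 12.1 states the comparison as reduction after 2 weeks, and a Day-14 contrast within a repeated-measures model is compatible with section 12. With only Day 0 and Day 14 in the model, the group-by-time F-test would equal the t-test on change, although a sphericity check points to more than two time points. The gap is one of specification, and this part of the objection stands.

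**The averaged effect may be the more powerful test.** A reader might also infer that the ANOVA must lose power. It need not: under AR(1) 0.5 the group effect beats Day-14 ANCOVA even with a linear profile. The only time course that the protocol describes (section 4.2, an earlier knee study) is early relief, within 3 days, that then persisted, which is nearer the plateau than the ramp. This also stands, with one reservation: power for an all-day average is power for a different quantity. The protocol also does not tie Day 1 to first use: section 9.2 starts assessment immediately, while section 15.2 has the device arriving in 3 to 5 days. If Day 1 follows enrolment, untreated days enter the average.

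**The inflated type I error is conditional.** It needs serially correlated errors, no correction and the omnibus test as decisive. The fair criticism is that a check is planned but no correction is named.

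**The precision gain has a different comparator.** The 15–35% is measured against an unadjusted Day-14 change score, which the SAP does not specify. It should not be read as the loss from the planned ANOVA.

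**Conclusion.** The point holds as under-specification with real consequences. The endpoint is a Day-14 contrast, and the primary method names neither that contrast, nor a deciding effect, nor a baseline covariate. The default tests would answer a different question. The averaged group effect would be 0.50 to 0.93 of the Day-14 effect across the linear, plateau and constant profiles, and either default test can be significant when the arms do not differ at Day 14. If the interaction decides without a correction, type I error is about 8–15% under serially correlated errors.

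All of these sizes rest on assumed profiles and correlations, and the power figures also on the assumed 0.6 SD effect. The gap between endpoint and method comes from the text alone. The direction and size of any power difference cannot be derived from the documents. The sham wording in SAP section 11.1 is a separate wording error that affects none of the figures.

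**What to change.** In SAP sections 12 and 12.1, name the device-minus-SOC difference in Day-14 change from baseline, with its 95% CI, as the primary estimate. Obtain it in one of two ways:

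- **ANCOVA** of the Day-14 score on arm and baseline score, which gives the same arm difference as for change and is the simpler choice; or
- **a mixed model for Days 1–14** with arm, day, arm-by-day and baseline terms, a parsimonious pre-stated covariance with robust errors, and a pre-specified Day-14 contrast. An unstructured covariance is not advisable: 14 × 15/2 = 105 parameters for at most 100 subjects.

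Keep any repeated-measures ANOVA as supportive, with a Greenhouse-Geisser correction. In SAP section 11.1, replace the reference to sham devices with the SOC comparator.

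The cost is SAP wording; no new data are needed. The one statistical downside is that a single-day contrast can have less power than the all-day average if the effect is early and constant (0.93 against 0.97 at r = 0.5 above). If the sponsor wants the average over days instead, the endpoint should be redefined to say so before the data are analysed.
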